**Version 1.0 of 27.9.2019**

*Protocol-specific version for protocol #PHS-  
ADHD-002-MEX- TAB, version 3.0 dated  
19.07.2019.*

**CONFIDENTIAL**

page 28 of 42

**Plan for statistical analysis of efficacy and safety parameters**

In the absence of data at Visit 4 when data are available at Visit 5, these patients will not be included in the FAS and PP populations, but will be analysed in the safety population.

In the presence of data at Visit 4 and the presence of the other listed significant protocol deviations, these patients will be included in the full analysis population, safety population, but excluded from the protocol population.

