#### **4.5.5. Visit 4 (Day 28±2), telephone contact**

Visit 4 takes the form of a telephone contact by the investigator 28 days from the start of treatment with the patient's parents. It is necessary to obtain information from parents about the general tolerability of therapy, adverse events that have occurred since the last evaluation, symptom scores according to the ADHD Rating Scale IV, concomitant medications prescribed, and remind them of compliance with therapy. If necessary, an unscheduled visit to the clinical site by the patient may be scheduled based on the information received, or a follow-up telephone contact may be scheduled at the discretion of the investigator to monitor adherence to recommendations.

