### ***10.2. Deviations from protocol***

In general, any deviation from the protocol may be accepted only in an urgent case or after obtaining written agreement from the Sponsor and subject to approval by the Ethics Committee. Any deviation from the protocol should be clearly explained in the source documentation and in the eCRF. Classification of protocol deviations will be made before the database cutt off by the Sponsor's medical expert. Deviations from the protocol will be considered significant in the following cases (the list may be expanded in a subsequent evaluation of protocol deviations):

- skip of visit 5;
- violation of inclusion / non-inclusion criteria;
- violation of the exclusion criteria;
- taking the Investigational product/placebo <80% or >120% of the total number of tablets prescribed;
- administration of prohibited drugs.

If significant deviations from the protocol are identified, the CRA must immediately inform the Sponsor.

In the absence of data at Visit 5 when data are available at Visit 6, these patients will not be included in the FAS and PP populations, but will be analysed in the safety population.

In the presence of data at Visit 5 and the presence of the other listed significant protocol deviations, these patients will be included in the full analysis population, safety population, but excluded from the protocol population.

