## **11. Patient populations to be analysed**

The following groups will be used for the analysis:

1. **Safety population** - will include all patients who have taken at least one dose of the investigational product;

2. **Full analysis set (FAS) population** - will include all randomized patients who have taken at least one dose of the investigational product and who have an assessed response to therapy after 6 weeks of therapy. This will be the main population for efficacy analyses;

3. **Per protocol population (PP)** is a subgroup of the FAS population that will include patients in the absence of significant protocol deviations regarding inclusion/non-inclusion criteria, adherence to therapy, and use of concomitant therapy. This will be an additional population used for efficacy analyses.

Efficacy analyses will be performed on the FAS population as well as on the PP population of all patients who completed the trial according to the protocol in order to validate the results obtained.

The final Clinical Trial Report will include data on all patients included in the trial, including those who dropped out at any time without explanation.

In general, any deviation from the protocol may be accepted only in an urgent case or after obtaining written agreement from the Sponsor and subject to approval by the Ethics Committee. Any deviation from the protocol should be clearly explained in the source documentation and in the eCRF. Classification of protocol deviations will be made by the Sponsor's medical expert before the database lock. Deviations from the protocol will be considered significant in the following cases (the list may be expanded in a subsequent evaluation of protocol deviations):

- skip of visit 4;
- violation of inclusion / non-inclusion criteria;
- violation of the exclusion criteria;
- taking the investigational product/placebo <80% or >120% of the total number of tablets prescribed;
- administration of prohibited drugs.

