## 12. Table templates

*Table 2. Results of assessment of normality of distribution of indicators (template)*

Indicators	Stage	Investigational products								
		Mexidol®			Placebo			Mexidol®+ Placebo		
		W	p	Distribution	W	p	Distribution	W	p	Distribution
Age	Visit 1 (Day-14-1)			normal/other than normal			normal/other than normal			normal/other than normal
Height	Visit 1 (Day-14-1)			normal/other than normal			normal/other than normal			normal/other than normal
Body weight	Visit 1 (Day-14-1)			normal/other than normal			normal/other than normal			normal/other than normal
BMI	Visit 1 (Day-14-1)			normal/other than normal			normal/other than normal			normal/other than normal
HR	Visit 1 (Day-14-1)			normal/other than normal			normal/other than normal			normal/other than normal
	Visit 4 (Day 43+1)			normal/other than normal			normal/other than normal			normal/other than normal
	Visit 5 (Day 50+3)			normal/other than normal			normal/other than normal			normal/other than normal
CHD	Visit 1 (Day-14-1)			normal/other than normal			normal/other than normal			normal/other than normal
	Visit 4 (Day 43+1)			normal/other than normal			normal/other than normal			normal/other than normal
	Visit 5 (Day 50+3)			normal/other than normal			normal/other than normal			normal/other than normal
Systolic BP	Visit 1 (Day-14-1)			normal/other than normal			normal/other than normal			normal/other than normal
	Visit 4 (Day 43+1)			normal/other than normal			normal/other than normal			normal/other than normal
	Visit 5 (Day 50+3)			normal/other than normal			normal/other than normal			normal/other than normal
Diastolic BP	Visit 1 (Day-14-1)			normal/other than normal			normal/other than normal			normal/other than normal
	Visit 4 (Day 43+1)			normal/other than normal			normal/other than normal			normal/other than
	Visit 5 (Day 50+3)			normal/other than normal			normal/other than normal			normal/other than normal
Haemoglobin	Visit 1 (Day-14-1)			normal/other than normal			normal/other than normal			normal/other than normal
	Visit 4 (Day 43+1)			normal/other than normal			normal/other than normal			normal/other than normal

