## Plan for statistical analysis of efficacy and safety parameters

Table 3. Statistical analysis of the primary endpoint (template)

Total score on the "inattention" and "hyperactivity/impulsivity" subscales of the SNAP IV scale	Mexidol®				Placebo				Mexidol®+ Placebo			
	Visit 2 (Day 1)	Visit 5 (Day 43+1)	Dynamics		Visit 2 (Day 1)	Visit 5 (Day 43+1)	Dynamics		Visit 2 (Day 1)	Visit 5 (Day 43+1)	Dynamics	
			Abs.	%			Abs.	%			Abs.	%
N												
Mean												
95% CI, L												
95% CI, U												
Median												
Min												
Max												
Q 1												
Q 3												
Range												
Q Range												
SD												
CV												
Intragroup comparison: comparison of data at the end of therapy with data at the start of therapy (statistical criterion  ) (p-level value)												
Comparison of drugs (statistical test  ) (p-value)												
Indicator span diagram/ indicator scatter diagram												

 T-test for related samples or Wilcoxon test depending on the type of distribution of the indicator T-test for independent samples or Mann-Whitney test depending on the type of distribution of the indicator

Version 1.0 of 27.9.2019

Protocol-specific version for protocol #PHS-ADHD-002-MEX- TAB,  
version 3.0 dated 19.07.2019.

CONFIDENTIAL

page 32 of 42

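### SAP 11 ties the FAS and PP sets to visit numbers that do not match Protocol v4.0, and the planned LOCF check has essentially no missing primary score to fill in any defined efficacy set

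*SAP*

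**What the plan says.** **Population rule.** SAP 11 lists "skip of visit 4" among the significant deviations and continues: "In the absence of data at Visit 4 when data are available at Visit 5, these patients will not be included in the FAS" or the PP set. A second sentence begins "In the presence of data at Visit 4 and the presence of the other listed significant protocol deviations"; it keeps such children in the full analysis and safety populations and removes them from PP. Protocol 10.2 states the first rule one visit later: "In the absence of data at Visit 5 when data are available at Visit 6, these patients will not be included in the FAS".

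**What the visits are.** In Protocol 4.5.5, "Visit 4 takes the form of a telephone contact by the investigator 28 days from the start of treatment". The schedule in 1.2 gives that call the ADHD Rating Scale-IV but no SNAP-IV. The only scheduled SNAP-IV after baseline is at Visit 5, the end-of-therapy visit around Day 43.

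**FAS definition.** SAP 11 admits randomised, dosed children "who have an assessed response to therapy after 6 weeks of therapy". The Protocol synopsis and 9.7 say the same. PP is a subset of the FAS.

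**Missing data.** SAP 6 plans a complete-case analysis and a post-hoc LOCF analysis, within a sensitivity analysis meant to show, among other things, the effect of missing values. Protocol 9.5 says missing data are not replaced. SAP 10 says so too, but in its safety section.

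**The concern.** The rule that defines the primary analysis population is correct only if the reader changes its visit numbers. The SAP cannot supply the correction consistently, because it labels Day 43 in two ways.

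The second part carries more weight. A child enters the FAS by having the outcome, so children who leave before week 6 are in no efficacy set. The one stated check on missing data is then applied where the primary score is not missing. If dropout were unequal and related to response, no planned analysis would show its effect on the primary comparison.

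**Working it through.** **1. Visit labels side by side**

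| Place | Day 28 | Day 43 | Day 50 |
|---|---|---|---|
| Protocol 1.2 and 4.5 | Visit 4 | Visit 5 | Visit 6 |
| SAP Table 2 | not shown | "Visit 4 (Day 43+1" | Visit 5 |
| SAP Tables 3, 4, 11 | not shown | "Visit 5 (Day 43+1" | not shown |
| SAP Tables 9, 10 | not shown | Visit 5 | Visit 6 |

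SAP 11 follows the Table 2 pattern. The primary-endpoint template (Table 3) follows the other. No single numbering makes the whole SAP consistent.

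**2. SAP 11 read literally with v4.0 numbers**

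- Child A missed the Day-28 call and has a Day-43 SNAP-IV. The FAS definition puts the child in; the first sentence takes the child out.
- Child B has Day-28 data, another listed significant deviation and no Day-43 score. The FAS definition takes the child out; the second sentence puts the child in.

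**3. The plan's sample size.** Inputs from Protocol 9.2: changes -4.5 (SD 7.515) and -2.0 (SD 4.70), difference 2.5, two-sided 0.05, power 80%, 10% dropout.

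- Pooled SD = sqrt((4.70² + 7.515²)/2) = 6.27.
- n = 2 × 6.27² × (1.96 + 0.8416)²/2.5² = 98.7, so 99 per arm; the noncentral t gives 100, as stated.
- At n = 100: SE = 6.27 × sqrt(2/100) = 0.887; power = Φ(2.5/0.887 - 1.96) = 0.805.
- Planned dropouts: 333 - 300 = 33.

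**4. What LOCF can fill.** In the FAS and in PP: essentially 0. A small exception is a child seen at week 6 with only this scale missing. In a set of all randomised, dosed children: about 33.

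**5. Worst case on that wider set.** Assume no early-termination score exists, so baseline is carried forward and the change is 0. With dropout share d, arm mean = (1-d)μ and variance = (1-d)(σ² + μ²) - ((1-d)μ)². N = 111 per arm.

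| Dropout active/placebo | Means | Difference | SE | Power |
|---|---|---|---|---|
| 10/10% (planned) | -4.05, -1.80 | 2.25 | 0.810 | 0.793 |
| 15/5% (assumed) | -3.825, -1.90 | 1.925 | 0.804 | 0.668 |
| 5/15% (assumed) | -4.275, -1.70 | 2.575 | 0.816 | 0.884 |

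**6. Selection with no drug effect.** Assume normal changes and that strictly the worst fraction p leaves each arm. The mean of those who stay is -φ(z)/(1-p) in SD units, with z the 1-p quantile. Active minus placebo:

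- 10/10%: 0.
- 12/8%: -0.227 + 0.162 = -0.066 SD, that is -0.31 points (SD 4.70) to -0.41 (SD 6.27).
- 15/5%: -0.274 + 0.109 = -0.166 SD, that is -0.78 to -1.04 points.

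**7. Placebo-based check.** If 10% of active children are given the placebo mean, the difference is 0.9 times the FAS difference. The smallest significant FAS difference is 1.96 × 0.887 = 1.74. With the SE held at 0.887, significance is lost only below 1.74/0.9 = 1.93.

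**8. Literal visit rule.** Each 1% of 300 completers who miss the call removes 3 children. The documents give no missed-call rate. At an assumed 2% to 10% (98 to 90 per arm), power is 0.797 to 0.763.

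**The case against.** **The numbering is editorial.** The SAP (27.09.2019) predates Protocol v4.0 (15.10.2019) and names v3.0 as its basis. A reader might infer that the SAP really removes children who have the primary score. The documents do not support that: the six-week clause in SAP 11, Table 2 and Protocol 10.2 all point to Day 43. This stands, so the power figures in step 8 describe an unintended reading. What remains is a rule that is wrong as written under the current protocol, in a SAP that disagrees with itself.

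**A wider set is hinted at.** Protocol 5.5 would use dropouts' data for efficacy where possible, 5.6 includes their data in the final analysis, and SAP 9 speaks of all included patients with at least one dose. SAP 6 does not restrict LOCF to the FAS, and it mentions an ITT population. But SAP 11 defines no efficacy set beyond FAS and PP, and ITT is undefined there; SAP 6's later account of the analysed populations suggests that FAS was meant.

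**LOCF need not mean baseline carried forward.** A reader might infer that it usually would. Protocol 4.5.9, 4.7 and 5.3 call for Visit 5 procedures at early termination, which include SNAP-IV. This stands, and step 5 is therefore a worst case. The gap is that no rule says whether such a score counts as the week-6 assessment. The windows also disagree: 4.5.6 rules out an earlier Visit 5, while the schedule in 1.2 gives Day 43±1.

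**Bias is not shown.** A reader might infer that the primary estimate will be biased. At equal dropout step 6 gives zero. Every non-zero figure there, at 12/8% as well as 15/5%, needs both unequal dropout and strictly the worst responders leaving.

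**Conclusion.** The point holds as one that should be fixed; it does not undermine the trial. The visit numbers in SAP 11 and Table 2 are wrong against Protocol v4.0, with no loss on the intended reading. The LOCF check cannot do its stated job in either defined efficacy set. It also conflicts with Protocol 9.5; the matching SAP 10 sentence need not govern efficacy.

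The count of about 33 children outside every efficacy set rests on the planned 10% dropout, and on early-termination scores not being taken as week-6 assessments. At equal dropout the numerical effect is small even in the worst case, and a placebo-based assumption would overturn significance only for a FAS difference between 1.74 and 1.93 points. Larger shifts, in either direction for baseline carried forward, rest on assumed dropout splits. The case for acting is that the plan has no working analysis that would reveal such a pattern.

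**What to change.** - In SAP 11 and Table 2, change Visit 4 to Visit 5 and Visit 5 to Visit 6, or refer to the Day-43 assessment. Reissue the SAP against Protocol v4.0.
- In SAP 6, replace ITT with FAS if that is what is meant, or define it.
- Define a set of all randomised children with at least one dose and a baseline SNAP-IV. Pre-specify the missing-data sensitivity analysis of the primary endpoint on it, rather than leaving it post hoc. One option is multiple imputation from baseline, the Day-28 ADHD Rating Scale-IV and early-termination SNAP-IV scores, with a placebo-based analysis beside it.
- State whether an early-termination SNAP-IV counts as the week-6 assessment, and how it is used otherwise.
- Reconcile Protocol 9.5 with SAP 6, and the Visit 5 window in Protocol 1.2 with 4.5.6. Align Protocol 5.5 and 5.6 with the population definitions.

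The FAS may stay the main set if the wider analysis is reported with it.

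**Cost.** A SAP reissue (Protocol 9.6 asks for approval only before database cut-off), some protocol wording and modest programming, with no new data collection. The imputation assumption must be justified. Little will be known about children who leave before Day 28 without a final examination. The estimate may come out slightly smaller.

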## 12. Table templates

*Table 2. Results of assessment of normality of distribution of indicators (template)*

Indicators	Stage	Investigational products								
		Mexidol®			Placebo			Mexidol®+ Placebo		
		W	p	Distribution	W	p	Distribution	W	p	Distribution
Age	Visit 1 (Day-14-1)			normal/other than normal			normal/other than normal			normal/other than normal
Height	Visit 1 (Day-14-1)			normal/other than normal			normal/other than normal			normal/other than normal
Body weight	Visit 1 (Day-14-1)			normal/other than normal			normal/other than normal			normal/other than normal
BMI	Visit 1 (Day-14-1)			normal/other than normal			normal/other than normal			normal/other than normal
HR	Visit 1 (Day-14-1)			normal/other than normal			normal/other than normal			normal/other than normal
	Visit 4 (Day 43+1)			normal/other than normal			normal/other than normal			normal/other than normal
	Visit 5 (Day 50+3)			normal/other than normal			normal/other than normal			normal/other than normal
CHD	Visit 1 (Day-14-1)			normal/other than normal			normal/other than normal			normal/other than normal
	Visit 4 (Day 43+1)			normal/other than normal			normal/other than normal			normal/other than normal
	Visit 5 (Day 50+3)			normal/other than normal			normal/other than normal			normal/other than normal
Systolic BP	Visit 1 (Day-14-1)			normal/other than normal			normal/other than normal			normal/other than normal
	Visit 4 (Day 43+1)			normal/other than normal			normal/other than normal			normal/other than normal
	Visit 5 (Day 50+3)			normal/other than normal			normal/other than normal			normal/other than normal
Diastolic BP	Visit 1 (Day-14-1)			normal/other than normal			normal/other than normal			normal/other than normal
	Visit 4 (Day 43+1)			normal/other than normal			normal/other than normal			normal/other than
	Visit 5 (Day 50+3)			normal/other than normal			normal/other than normal			normal/other than normal
Haemoglobin	Visit 1 (Day-14-1)			normal/other than normal			normal/other than normal			normal/other than normal
	Visit 4 (Day 43+1)			normal/other than normal			normal/other than normal			normal/other than normal

**Version 1.0 of 27.9.2019**

Protocol-specific version for protocol #PHS-ADHD-002-MEX- TAB, version 3.0 dated 19.07.2019.

**CONFIDENTIAL**

page 29 of 42

## Plan for statistical analysis of efficacy and safety parameters

Indicators	Stage	Investigational products								
		Mexidol®			Placebo			Mexidol®+ Placebo		
		W	p	Distribution	W	p	Distribution	W	p	Distribution
Haematocrit	Visit 1 (Day -14-1)			normal/other than normal			normal/other than normal			normal/other than normal
	Visit 4 (Day 43+1)			normal/other than normal			normal/other than normal			normal/other than normal
Erythrocyte count	Visit 1 (Day -14-1)			normal/other than normal			normal/other than normal			normal/other than normal
	Visit 4 (Day 43+1)			normal/other than normal			normal/other than normal			normal/other than normal
Platelet count	Visit 1 (Day -14-1)			normal/other than normal			normal/other than normal			normal/other than normal
	Visit 4 (Day 43+1)			normal/other than normal			normal/other than normal			normal/other than normal
White blood cell count	Visit 1 (Day -14-1)			normal/other than normal			normal/other than normal			normal/other than normal
	Visit 4 (Day 43+1)			normal/other than normal			normal/other than normal			normal/other than normal
Eosinophils	Visit 1 (Day -14-1)			normal/other than normal			normal/other than normal			normal/other than normal
	Visit 4 (Day 43+1)			normal/other than normal			normal/other than normal			normal/other than normal
Basophils	Visit 1 (Day -14-1)			normal/other than normal			normal/other than normal			normal/other than normal
	Visit 4 (Day 43+1)			normal/other than normal			normal/other than normal			normal/other than normal
Stab neutrophils	Visit 1 (Day -14-1)			normal/other than normal			normal/other than normal			normal/other than normal
	Visit 4 (Day 43+1)			normal/other than normal			normal/other than normal			normal/other than normal
Segmented neutrophils	Visit 1 (Day -14-1)			normal/other than normal			normal/other than normal			normal/other than normal
	Visit 4 (Day 43+1)			normal/other than normal			normal/other than normal			normal/other than normal
Lymphocytes	Visit 1 (Day -14-1)			normal/other than normal			normal/other than normal			normal/other than normal
	Visit 4 (Day 43+1)			normal/other than normal			normal/other than normal			normal/other than normal
Monocytes	Visit 1 (Day -14-1)			normal/other than normal			normal/other than normal			normal/other than normal
	Visit 4 (Day 43+1)			normal/other than normal			normal/other than normal			normal/other than normal
ESR	Visit 1 (Day -14-1)			normal/other than normal			normal/other than normal			normal/other than normal
	Visit 4 (Day 43+1)			normal/other than normal			normal/other than normal			normal/other than normal
Total protein	Visit 1 (Day -14-1)			normal/other than normal			normal/other than normal			normal/other than normal

Version 1.0 of 27.9.2019

Protocol-specific version for protocol #PHS-ADHD-002-MEX- TAB, version 3.0 dated 19.07.2019.

CONFIDENTIAL

page 30 of 42

## Plan for statistical analysis of efficacy and safety parameters

Indicators	Stage	Investigational products								
		Mexidol®			Placebo			Mexidol®+ Placebo		
		W	p	Distribution	W	p	Distribution	W	p	Distribution
	Visit 4 (Day 43+1)			normal/other than normal			normal/other than normal			normal/other than normal
Albumin	Visit 1 (Day -14-1)			normal/other than normal			normal/other than normal			normal/other than normal
	Visit 4 (Day 43+1)			normal/other than normal			normal/other than normal			normal/other than normal
Glucose	Visit 1 (Day -14-1)			normal/other than normal			normal/other than normal			normal/other than normal
	Visit 4 (Day 43+1)			normal/other than normal			normal/other than normal			normal/other than normal
ALT	Visit 1 (Day -14-1)			normal/other than normal			normal/other than normal			normal/other than normal
	Visit 4 (Day 43+1)			normal/other than normal			normal/other than normal			normal/other than normal
AST	Visit 1 (Day -14-1)			normal/other than normal			normal/other than normal			normal/other than normal
	Visit 4 (Day 43+1)			normal/other than normal			normal/other than normal			normal/other than normal
Total bilirubin	Visit 1 (Day -14-1)			normal/other than normal			normal/other than normal			normal/other than normal
	Visit 4 (Day 43+1)			normal/other than normal			normal/other than normal			normal/other than normal
Alkaline phosphatase (ALP)	Visit 1 (Day -14-1)			normal/other than normal			normal/other than normal			normal/other than normal
	Visit 4 (Day 43+1)			normal/other than normal			normal/other than normal			normal/other than normal
Amylase	Visit 1 (Day -14-1)			normal/other than normal			normal/other than normal			normal/other than normal
	Visit 4 (Day 43+1)			normal/other than normal			normal/other than normal			normal/other than normal
Creatinine	Visit 1 (Day -14-1)			normal/other than normal			normal/other than normal			normal/other than normal
	Visit 4 (Day 43+1)			normal/other than normal			normal/other than normal			normal/other than normal
Urine pH	20 weeks			normal/other than normal			normal/other than normal			normal/other than normal
	24 weeks			normal/other than normal			normal/other than normal			normal/other than normal
Urine specific gravity	28 weeks			normal/other than normal			normal/other than normal			normal/other than normal
	32 weeks			normal/other than normal			normal/other than normal			normal/other than normal

